#### 4.4. Other Endpoints Analyses

**CCI**

#### 4.5. Safety Analyses

All safety summaries and listings will be produced for the Safety Analysis Set unless otherwise specified. All safety summaries will be presented overall and by the treatment in the previous study.

##### 4.5.1. Extent of Exposure

Two doses of open-label study treatment will be administered during treatment period: Visit 1 (Day1/Week 0) and the second at Visit 6 (Week 26). Each dose is viewed as providing therapeutic coverage for 26 weeks (182 days). The number of treatments administered and the number of days exposure in this study will be summarised descriptively and listed. Total subject-year exposure in this study will also be presented.

Number of days of exposure to study treatment in this study will be calculated as follows:

Duration of Exposure in Days = (Date of Final Dose) – (Date of First Dose) + 182

Subject years exposure in this study is calculated as follows:

Subject Years Exposure = ((Date of Final Dose) – (Date of First Dose) + 182)/365.25

The exposure summary will also be presented by age subgroup (12-17, 18-64,  $\geq 65$ ).

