4.4. End of Study Definition

The end of the study is defined as the date of the last follow-up visit/call for the last participant in the trial.

Participants will be considered to have completed the study if he/she has completed the Exit Visit and the Follow-up visit/call, 4 weeks after the Exit Visit, regardless of whether the second dose of study intervention (at Week 26) was received.

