## 4.9. Interim Analyses

### 4.9.1. Interim Analysis for Regulatory Submission

As the study will be still ongoing at the time of regulatory submission, interim analyses will be performed in order to provide open-label safety and efficacy data in an interim Clinical Study Report (CSR) to inform the risk-benefit assessment of GSK3511294 in asthma with an eosinophilic phenotype..

At interim a ‘cut’ will be made in the data, where any data collected beyond a prespecified cut-off date will not be included within the datasets to be reported. The interim analysis will include the analyses specified in this analysis plan. The details of the outputs are in the OPS.

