#### 6.1.1. Participant Disposition

A summary of the number and percentage of participants who completed the study as well as those who prematurely withdrew from the study will be provided. Reasons for study withdrawal will be summarised. For those who have neither completed nor withdrawn, they will be categorized as on study intervention or in follow up.

A summary of study intervention status will be provided. This display will show the number and percentage of participants who have completed the scheduled study intervention, are ongoing with study intervention, or have discontinued study intervention prematurely, as well as primary reasons for discontinuation of study intervention.

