### 6.2.2.3. Study Treatment Flag for Adverse Events

Study Phase	Definition
Pre-Treatment	AE start date $<$ Study Treatment Start Date
On-Treatment	Study Treatment Start Date $\leq$ AE start date $\leq$ Date of Last Dose + 182 days
Post-Treatment	AE start date $>$ Date of Last Dose + 182 days

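### The exposure formula credits a full 182 days after the last dose, with no stop at the interim data cut-off or at death, so it can count time that has not occurred

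*SAP*

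**What the plan says.** SAP 4.5.1 rests exposure on a coverage convention: "Each dose is viewed as providing therapeutic coverage for 26 weeks (182 days"). Days of exposure are the final dose date minus the first dose date plus 182, and the person-time version is "Subject Years Exposure = ((Date of Final Dose) – (Date of First Dose) + 182)/365.25". The section adds: "Total subject-year exposure in this study will also be presented". It gives no rule for a participant who has died, or whose 182 days have not elapsed when the data are cut.

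SAP 4.9.1 describes an interim analysis for regulatory submission while the study is ongoing. At that point "any data collected beyond a prespecified cut-off date will not be included within the datasets to be reported", and "The interim analysis will include the analyses specified in this analysis plan". It leaves output details to the Output and Programming Specification (OPS) and states no separate exposure rule for the interim.

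The on-treatment window for adverse events in SAP 6.2.2.3 ends at the same point, "Date of Last Dose + 182 days". SAP 6.1.1 provides for participants still under way: "For those who have neither completed nor withdrawn, they will be categorized as on study intervention or in follow up".

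**The concern.** The coverage convention is reasonable for a living participant whose 182 days have passed, even if contact was lost. It cannot justify counting days after death, or days after the cut-off that nobody has yet lived through.

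The cut removes collected records. The 182 days are not a record, so they survive it. Exposure then runs past the cut-off while events cannot, although both are defined by the same endpoint of last dose plus 182 days.

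This is primarily a long-term safety study, and the interim report is meant to inform the risk-benefit assessment. A reader will take total subject-years as safety experience already accrued. An AE/SAE incidence rate is also a primary summary measure (Protocol 9.4.2, SAP 1.1.2), but SAP 4.5.2 names no denominator for it. If the uncapped total were used, those rates would come out too low.

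**Working it through.** **Inputs.** Coverage per dose is 182 days (SAP 4.5.1; 26 × 7 = 182). Doses are at Week 0 and Week 26, so the second is at day 182. N = 637 is the protocol's enrolment assumption (Protocol 9.2), used only to turn percentages into subject-years. Accrual pace and the cut-off date are not in the documents and are assumed below.

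**The plan's own rule.** One dose: 182 days, 182/365.25 = 0.498 years. Two doses on time: 182 + 182 = 364 days, 0.997 years. Full total: 637 × 364/365.25 = 634.8 subject-years.

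**Individual participants.** Elapsed exposure is min(last dose + 182, cut-off, death) − first dose.

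| Situation | Credited (days) | Elapsed (days) | Excess (days) |
|---|---|---|---|
| One dose, 30 days before cut-off | 182 | 30 | 152 |
| One dose, 91 days before | 182 | 91 | 91 |
| Second dose 14 days before | 364 | 196 | 168 |
| Second dose 91 days before | 364 | 273 | 91 |
| Second dose 182 or more days before | 364 | 364 | 0 |
| Death 60 days after a single dose | 182 | 60 | 122 |

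**Scenario 1: a share p is within 182 days of the last dose, spread evenly over days 0 to 364 since the first dose; the rest are complete.** An affected participant is credited (182 + 364)/2 = 273 days on average, against 182 elapsed. Overstatement = [273p + 364(1 − p)] / [182p + 364(1 − p)] − 1. Excess subject-years = 637 × 91p / 365.25.

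| p | Credited mean | Elapsed mean | Overstatement | Excess subject-years |
|---|---|---|---|---|
| 0 | 364 | 364 | 0% | 0 |
| 0.10 | 354.9 | 345.8 | 2.6% | 16 |
| 0.25 | 341.25 | 318.5 | 7.1% | 40 |
| 0.50 | 318.5 | 273 | 16.7% | 79 |
| 1 | 273 | 182 | 50% | 159 |

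**Scenario 2: everyone has had the second dose, and a share p is within 182 days of it, evenly spread.** Affected participants are credited 364 days against 273. Overstatement = 364 / [273p + 364(1 − p)] − 1, giving 2.6%, 6.7% and 14.3% for p = 0.10, 0.25 and 0.50.

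**Scenario 3: uniform accrual.** Time since first dose t is cut-off minus enrolment (t > 0). Credited days are 182 if t < 182, otherwise 364; elapsed days are min(t, 364); one month is 30.4375 days. For 12-month accrual cut at 18 months, the means are 364.0 and 319.0, so 364.0/319.0 − 1 = 14.1%.

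| Accrual (months) | Overstatement, by cut-off in months after first enrolment |
|---|---|
| 6 | 32.9% (12), 6.5% (15), 0% (18) |
| 12 | 49.7% (12), 21.6% (15), 14.1% (18), about 3% (21), 0% (24) |
| 18 | 24.9% (18), 9.0% (24), 2.1% (27), 0% (30) |
| 24 | 16.6% (24), 6.6% (30), 0% (36) |

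**Effect on a rate, if this total were its denominator.** Understatement is 1 − elapsed/credited. For the 14.1% case it is 1 − 319.0/364.0 = 12.4%.

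**Final analysis.** A death at a uniformly distributed time in the 182 days after the last dose adds 91/365.25 = 0.25 subject-years on average, at most 182/365.25 = 0.50, out of about 635.

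**The case against.** The strongest reply is that 4.5.1 declares a convention: exposure means drug coverage delivered, not time observed, and the same 26 weeks defines the while-on-treatment strategy and the adverse event window. On that reading a cap would change the quantity being reported. This holds for a living participant lost to contact, and the fix below leaves that case alone. It does not hold for days after death or after the cut-off.

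A second reply is that the OPS, which is not available here, may contain a cap. That cannot be excluded. But SAP 4.9.1 leaves only output details to the OPS, and the SAP itself states the derivation in full.

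Third, the harm is conditional, and this stands. Under Protocol 4.4, "The end of the study is defined as the date of the last follow-up visit/call for the last participant in the trial", so the study can still be open when every participant is past 182 days, with no overstatement. No hypothesis is tested. The number of doses given and participant disposition are also displayed, so a reader could see that follow-up is incomplete, though not correct the total.

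Fourth, the illustrations depend on their assumptions. The largest scenario 3 figures for accrual of 12 months or more put the cut-off on the day accrual closes. The 50% in scenario 1 follows from an even spread over 364 days and is not a general ceiling: with everyone spread evenly over the first 182 days the ratio is 182/91, an overstatement of 100%. The Safety set excludes three sites, so subject-years based on 637 are indicative only; the percentages do not depend on N.

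Finally, the missing rate denominator is a separate omission, and the case for capping exposure does not depend on it.

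**Conclusion.** The concern holds. Followed as written, the SAP counts exposure that has not occurred for anyone less than 182 days past the last dose at the interim cut-off, and for anyone who dies within 182 days of the last dose. The absence of a cap in the SAP is certain. Its numerical effect is not: it runs from zero upwards, at 2.6% to 16.7% for affected shares of 10% to 50% in scenario 1, and more if the cut-off comes early relative to accrual.

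The consequence is confined mainly to interim subject-years. Percentages of participants with adverse events do not change. Rates would be understated only if this total became their denominator, which no document states. At the final analysis the effect on the exposure total is about 0.04% per death (0.25/635). The point should be fixed before the interim report is produced.

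**What to change.** In SAP 4.5.1, keep the 26-week coverage convention but end exposure at the earliest of last dose + 182 days, death and data cut-off, for both days and subject-years.

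In SAP 4.5.2, add a sentence naming the denominator of the AE/SAE incidence rates as at-risk time, ending at the earliest of last dose + 182 days, death, data cut-off and last contact. Last contact belongs here because events cannot be recorded after it. If 1% to 5% of participants were lost unobserved, half in each dosing interval, leaving it out would inflate at-risk time by 0.3% to 1.3%; Protocol 7.2 expects withdrawal to be uncommon.

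The cost is one derivation line and one sentence, with no new data. Interim subject-years will be smaller if participants are still within 182 days of a dose, and exposure and at-risk time become two quantities that need separate labels. If nobody is affected, the exposure results do not change.

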#### 4.5.2. Adverse Events

Adverse events analyses including the analysis of adverse events (AEs), Serious AEs (SAEs) and other significant AEs will be based on GSK Core Data Standards.

Adverse events will be coded using the standard Medical Dictionary for Regulatory Activities (MedDRA dictionary).

An overview summary of AEs, including counts and percentages of participants with any AE, AEs related to study intervention, AEs leading to permanent discontinuation of study intervention or withdrawal from study, study intervention related AEs leading to permanent discontinuation of study intervention or withdrawal from study, SAEs, SAEs related to study intervention, fatal SAEs, and fatal SAEs related to study intervention will be produced.

A summary of number and percentage of participants with any adverse events by maximum severity will be produced.

The frequency and percentage of AEs will be summarised in two ways: 1) in descending order by System Organ Class (SOC) and Preferred Term (PT). 2) in descending order by PT only.

Common ( $\geq 3\%$ ) AEs will be summarised by overall frequency and summarised by time to onset.

A separate summary will be provided for study intervention-related AEs. A study intervention-related AE is defined as an AE for which the investigator classifies the possible relationship to study intervention as “Yes”. A worst-case scenario approach will be taken to handle missing relatedness data, i.e. the summary table will include events with the relationship to study intervention as ‘Yes’ or missing.

All SAEs will be tabulated based on the number and percentage of participants who experienced the event. Separate summaries will also be provided for study intervention-related SAEs. The summary tables will be displayed in descending order by System Organ Class (SOC) and Preferred Term (PT).

A study intervention-related SAE is defined as an SAE for which the investigator classifies the relationship to study intervention as “Yes”. A worst-case scenario approach will be taken to handle missing data, i.e. the summary table will include events with the relationship to study intervention as ‘Yes’ or missing.

AE/study intervention related AE/SAE/etc will be summarised separately according to study treatment phases.

Summary table	Pre-treatment	On Treatment	On and Post treatment	Pre, on and Post treatment
AEs by SOC and PT		✓	✓	
Common AEs ( $\geq 3\%$ ) by overall frequency		✓		

Summary table	Pre-treatment	On Treatment	On and Post treatment	Pre, on and Post treatment
Drug related AE by SOC and PT		✓	✓	
SAE by SOC and PT	✓	✓	✓	
Drug related SAE by SOC and PT			✓	
Drug related SAE by overall frequency			✓	
Drug related fatal by SOC and PT			✓	
Drug related non-serious AE by overall frequency			✓	
Adverse Events of Special Interest (AESI)		✓	✓ Only single summary	
Summary of Deaths				✓
COVID-19 AEs		✓		

Note: study treatment phases are defined in Section [6.2.2](#).

#### 4.5.2.1. Adverse Events of Special Interest

Adverse events of special interest (AESI) for GSK3511294 program include:

- Allergic (Type 1 hypersensitivity) reactions including anaphylaxis

Note: these events will be assessed by the investigator as to whether they meet the diagnostic criteria for anaphylaxis as outlined by the 2006 Joint NIAID/FAAN Second Symposium on Anaphylaxis [[Sampson](#), 2006]

- Type III hypersensitivity (immune complex disease/vasculitis) reactions
- Local injection site reactions
- QTc prolongation

AESI reported by the investigator as systemic reactions (further categorised by the investigator as either allergic [type I hypersensitivity] or other systemic reactions and assessed against Sampson criteria for anaphylaxis) are collected via targeted eCRF within the study. Vasculitis events and local injection site reactions are also collected via targeted eCRF within the study.

Separate summary tables showing the number and percent of subjects with each type of AESI (excluding QTc prolongation) broken down by PT will be created.

For each type of AESI (excluding QTc prolongation) a profile summary table will be produced containing information including, but not limited to, the number of occurrences of the event, event characteristics, time to onset, intensity, outcome and action taken.

AESI of QTc prolongation will be summarised as detailed in Section [4.5.3.3](#) ECG.

Additionally, AESI of QTc prolongation will be summarised using the MedDRA SMQ Broad “Torsade de pointes/QT Prolongation” by overall and by the treatment in the previous study, for the program level analysis. The display will include both an “Any Event” row and the individual PTs.

#### **4.5.2.2. COVID-19 Assessment and COVID-19 AEs**

A standardized MedDRA Query (SMQ) will be used to identify all COVID-19 AEs.

The overall incidence of AEs and SAEs of COVID-19, COVID-19 AEs leading to study intervention discontinuation and COVID-19 AEs leading to study withdrawal will be summarised. The incidence of these events at individual PT level can be obtained from the standard AE/SAE summaries.

#### **4.5.2.3. Impact of COVID-19 Pandemic on Safety Results**

The impact of the COVID-19 pandemic on the safety results will be assessed. Subject status and subject disposition for the study conclusion record by relationship to COVID-19 pandemic, treatment status and reasons for discontinuation of study treatment by relationship to COVID-19 pandemic, important COVID-19 related protocol deviations, visits impacted by COVID-19 pandemic will be summarised.

COVID-19-related adverse events by System Organ Class and Preferred Term, COVID-19 assessments for subjects with COVID-19 adverse events will be summarised.

### **4.5.3. Additional Safety Assessments**

#### **4.5.3.1. Laboratory Data**

Summaries of worst-case changes from baseline with respect to normal range will be generated. Decreases to low, changes to normal or no changes from baseline, and increases to high will be summarised for the worst-case post-baseline. If a subject has a decrease to low and an increase to high during the same time interval, then the subject is counted in both the “Decrease to Low” categories and the “Increase to High” categories.

Separate summary tables for haematology, and chemistry laboratory tests will be produced. Liver function laboratory tests will be included with chemistry lab tests.

Summaries of hepatobiliary laboratory events including possible Hy’s law cases will be provided in addition to what has been described above. Possible Hy’s law cases are defined as any elevated alanine aminotransferase (ALT)>3×upper limit of normal (ULN), total bilirubin≥2×ULN and alkaline phosphatase (ALP)<3×ULN/missing. Total bilirubin≥2×ULN can be within 28 days following the ALT elevation and if direct bilirubin is available on the same day, it must be ≥ 35% of total bilirubin.

ALP<3×ULN/missing means it is satisfied unless the ALP is ≥3xULN at the time of bilirubin elevation. The summary will be produced for worst case post baseline only.

An e-DISH plot of maximum post baseline total bilirubin versus maximum post baseline ALT will be created.

Samples for anti-MPO antibody, anti-PR3 antibody, ANA, and anti-dsDNA antibody are collected at baseline visit of previous study (206713 or 213744) and if clinically indicated post baseline (in this study), analysed on as needed basis and will be summarised only for participants with data available.

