| Pregnancy testing | 
 Highly sensitive urine pregnancy test at Visit 1 and as per SoA (Section 1.3) during study intervention period and at the Follow up Visit for WOCBP⁴; Highly sensitive serum pregnancy test at Exit Visit of 206713/213744 study for all WOCBP. | | | |

NOTES:

ALT = Alanine Aminotransferase; AST = Aspartate Aminotransferase; BUN = Blood urea nitrogen; FSH = Follicle-stimulating hormone; GGT = Gamma glutamyl transferase; hBsAg – hepatitis B surface antigen; hBc = hepatitis B core antibody; hCG = human chorionic gonadotropin; hsCRP = highly sensitive C-reactive protein; MPO = myeloperoxidase; PR3 = proteinase 3; RBC = red blood cell; SGOT = Serum Glutamic-Oxaloacetic Transaminase; SGPT = Serum Glutamic-Pyruvic Transaminase; UACR = urinary albumin-creatinine ratio; WBC = white blood cell; WOCBP = women of childbearing potential; WONCBP = women of non-childbearing potential.

1. To maintain the treatment blind, the following post-dose results will not be reported to investigators and blinded Sponsor representatives: absolute and percentage values of eosinophils, neutrophils, lymphocytes, monocytes, and basophils (Unblinded at CCI [REDACTED])
2. Details of liver chemistry stopping criteria and required actions and follow-up assessments after liver stopping or monitoring event are given in Section 7.1 and Section 10.6. All events of $ALT \geq 3 \times$ upper limit of normal (ULN) and total bilirubin $\geq 2 \times$ ULN ($>35\%$ direct bilirubin) or $ALT \geq 3 \times$ ULN and international normalized ratio (INR) >1.5 , if INR measured, which may indicate severe liver injury (possible Hy's Law), must be reported to GSK as an SAE.
3. If alkaline phosphatase is elevated, consider fractionating.
4. Local urine testing will be standard for the protocol unless serum testing is required by local regulation or IRB/IEC.

10.3. Appendix 3: AEs and SAEs: Definitions and Procedures for Recording, Evaluating, Follow-up, and Reporting

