10.3.2. Definition of SAE

If an event is not an AE per definition above, then it cannot be an SAE even if serious conditions are met (e.g., hospitalization for signs/symptoms of the disease under study, death due to progression of disease, etc.).

An SAE is defined as any untoward medical occurrence that, at any dose, meets one or more of the criteria listed:

a) Results in death

b) Is life-threatening

The term 'life-threatening' in the definition of 'serious' refers to an event in which the participant was at risk of death at the time of the event. It does not refer to an event, which hypothetically might have caused death, if it were more severe.

c) Requires inpatient hospitalization or prolongation of existing hospitalization

- In general, hospitalization signifies that the participant has been admitted (usually involving at least an overnight stay) at the hospital or emergency ward for observation and/or treatment that would not have been appropriate in the physician's office or outpatient setting. Complications that occur during hospitalization are AE. If a complication prolongs hospitalization or fulfils any other serious criteria, the event is serious. When in doubt as to whether "hospitalization" occurred or was necessary, the AE should be considered serious.
- Hospitalization for elective treatment of a pre-existing condition that did not worsen from baseline is not considered an AE.

An SAE is defined as any untoward medical occurrence that, at any dose, meets one or more of the criteria listed:

d) Results in persistent or significant disability/incapacity

- The term disability means a substantial disruption of a person's ability to conduct normal life functions.
- This definition is not intended to include experiences of relatively minor medical significance such as uncomplicated headache, nausea, vomiting, diarrhoea, influenza, and accidental trauma (e.g. sprained ankle) which may interfere with or prevent everyday life functions but do not constitute a substantial disruption.

e) Is a congenital anomaly/birth defect

f) Other situations:

- Possible Hy's Law case: $ALT \geq 3 \times ULN$ AND total bilirubin $\geq 2 \times ULN$ ($> 35\%$ direct bilirubin) or international normalised ratio (INR) > 1.5 must be reported as SAE

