**Laboratory Values**

Haematology				
Laboratory Parameter	Units	Category	Clinical Concern Range	
			Low Flag (< x)	High Flag (>x)
CCI				

Clinical Chemistry				
Laboratory Parameter	Units	Category	Clinical Concern Range	
			Low Flag (< x)	High Flag (>x)
Calcium	mmol/L	3+ years	1.50	3.24
Creatinine	Umol/L	12+ years		>5 x ULN
Glucose	mmol/L	1+ years	2.2	27.8
Potassium	mEq/L	3+ years	2.8	6.5
Magnesium	mmol/L	6+years	0.3	2.5
Phosphorus	mmol/L	3+years	0.32	
Sodium	mEq/L	0+ years	120	160
ALT	U/L	12+ years		>239
Creatine Phosphokinase	IU/L	12+years		>5xULN

Liver Function				
Laboratory Parameter	Units	Category	Clinical Concern Range	
			High Flag (>x)	
ALT/SGPT	U/L	High	3 x ULN	
AST/SGOT	U/L	High	3 x ULN	
AlkPhos	U/L	High	3 x ULN	
T Bilirubin	µmol/L	High	34.2	
ALT, Bilirubin	U/L		ALT $\geq$ 3xULN and Bilirubin $\geq$ 2xULN (>35% direct)	
ALT, INR			ALT $\geq$ 3xULN and INR > 1.5	

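### The SAP's possible Hy's law row uses a different rule from the protocol's definition of the same term, so it can omit cases that the protocol requires as SAEs

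*SAP*

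**What the plan says.** **Protocol.** The definition appears in three places and is consistent in substance: Section 10.3.2 (SAE definition, other situations), Appendix 2 (Table 3, note 2) and Appendix 6 (footnote 2 to the stopping criteria). Section 10.3.2 opens with "Possible Hy's Law case: $ALT \geq 3 \times ULN$ AND total bilirubin" and gives the alternative route as "direct bilirubin) or international normalised ratio (INR") above 1.5. Appendix 2 spells out that the INR route also needs ALT of at least 3×ULN, and says that such events "must be reported to GSK as an SAE". None of the three has an ALP condition. Appendix 6 adds that the INR threshold does not apply to participants on anticoagulants.

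**SAP 4.5.3.1.** Summaries of hepatobiliary laboratory events will include possible Hy's law cases. These need ALT strictly above 3×ULN, plus "total bilirubin≥2×ULN and alkaline phosphatase (ALP)<3×ULN/missing". The ALP limb "means it is satisfied unless the ALP is ≥3xULN at the time of bilirubin elevation". Bilirubin may rise up to 28 days after ALT, and "if direct bilirubin is available on the same day, it must be ≥ 35% of total bilirubin". INR is not mentioned.

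**SAP 6.2.1.** The liver function flags for potential clinical importance include ALT of at least 3×ULN with bilirubin of at least 2×ULN (more than 35% direct), and separately ALT of at least "3xULN and INR > 1.5". Neither flag carries an ALP condition or is linked to the summary in 4.5.3.1.

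**SAP 4.10** lists no changes to protocol-defined analyses.

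**The concern.** The same label is attached to two different rules. A participant whose event is reported as a possible Hy's law SAE under the protocol may not be counted in the laboratory row that carries that name. This is a safety study in which hepatobiliary laboratory abnormalities are a listed endpoint (under Other), and the same analyses feed the interim CSR for the regulatory submission. A reader who finds no possible Hy's law case in the laboratory summary, and one among the SAEs, would have nothing in the SAP to explain the difference.

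**Working it through.** The plan gives no figure to reproduce, so the check compares the two rules.

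**Limb by limb**

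| Element | Protocol 10.3.2, Appendices 2 and 6 | SAP 4.5.3.1 | Effect on the SAP row |
|---|---|---|---|
| ALT | ≥3×ULN | >3×ULN | omits ALT of exactly 3×ULN |
| Bilirubin | ≥2×ULN | ≥2×ULN | none |
| Direct fraction | >35% | ≥35%, only if available the same day | admits exactly 35%, and missing |
| ALP | no condition | <3×ULN or missing | omits ALP ≥3×ULN at the bilirubin rise |
| INR >1.5 with raised ALT | sufficient (not if on anticoagulants) | absent | omits cases that qualify by INR alone |
| Timing | none stated | bilirubin within 28 days after ALT | makes the pairing explicit |

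**Worked profiles** (multiples of ULN; bilirubin concurrent with ALT; no anticoagulant)

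| | ALT | Bilirubin | Direct | INR | ALP | Protocol | SAP 4.5.3.1 |
|---|---|---|---|---|---|---|---|
| A | 5 | 1.2 | 20% | 1.8 | 1 | yes | no |
| B | 5 | 3 | 60% | 1.1 | 3.5 | yes | no |
| C | 3.0 | 2.5 | 50% | 1.0 | 1 | yes | no |
| D | 5 | 3 | 35% | 1.0 | 1 | no | yes |
| E | 5 | 3 | missing | 1.0 | 1 | no | yes |
| F | 5 | 3 | 60% | 1.0 | 1 | yes | yes |

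Profile E reads the protocol literally, as needing a known direct fraction above 35%.

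**Do the differences act independently?** Both rules were applied to every combination of ALT 2.9, 3.0, 3.1, 6.0; bilirubin 1.0, 2.0, 2.5; direct fraction missing, 30, 35, 36%; INR missing, 1.0, 1.6; and ALP missing, 1.0, 3.0, 4.0. That is 4×3×4×3×4 = 576 profiles.

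- 192 meet the protocol rule. The SAP rule catches 40 of these and misses 192 − 40 = 152.
- Of the 152 misses, 24 are due to the INR route alone, 24 to ALP alone and 12 to ALT of exactly 3×ULN alone. The other 152 − 60 = 92 combine two or three of these.
- 32 profiles meet only the SAP rule: 16 with direct fraction missing and 16 at exactly 35%.

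The values were chosen to sit on the boundaries. The counts show that each difference can remove a case by itself and that neither rule contains the other. They say nothing about how often this will happen.

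**Can the omitted cases arise?** ALP is in the routine chemistry panel (Protocol Table 3), so the ALP exclusion can operate. INR is not in that panel, but Appendix 6 calls for it in participants who meet liver stopping criteria and in the weekly repeat tests under increased monitoring. INR values should therefore exist for many of the participants in whom the route matters.

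**The case against.** The strongest defence is that the two rules do different jobs. The protocol's is an investigator's trigger for SAE reporting. The SAP's is a programmed laboratory summary, and an ALP-restricted version is a legitimate display. The protocol prescribes no Hy's law analysis and leaves other endpoints to the SAP (Section 9.4.4), so the entry under SAP 4.10 is not clearly breached. This stands as far as it goes: the ALP-restricted rule may be shown. It does not justify giving it, without comment, a name that the protocol defines otherwise.

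Several stronger readings are tempting, and the documents do not support them:

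- *That cases disappear from safety reporting.* SAP 4.5.2 tabulates all SAEs. The e-DISH plot of maximum bilirubin against maximum ALT has no stated ALP condition, so it would show high-ALP cases. It would not identify INR-route cases, and SAE tables by organ class and preferred term do not correct the Hy's law count.
- *That the SAP rule is simply narrower.* It is narrower on ALT, ALP and INR, but wider on direct bilirubin.
- *That the SAP defines Hy's law twice.* Section 6.2.1 never uses the term. Its rows are clinical-importance flags, and they show that the SAP already plans to derive both protocol criteria.
- *That the whole hepatobiliary table is deficient.* Only the possible Hy's law row is shown to differ. Other rows may be set out in the Output and Programming Specification, which is not available here.

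**Conclusion.** The mismatch is real and confined to one row. As written, the possible Hy's law count can omit INR-route cases and cases with ALP of at least 3×ULN at the bilirubin rise. These two differences carry the point; the ALT boundary is trivial.

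The number affected is likely to be very small. Section 5.2 excludes ALT above 2×ULN, most bilirubin above 1.5×ULN and unstable liver or biliary disease at entry, and INR is measured only selectively. The documents give no event rates from which to estimate a number. No inference changes, since the study has no hypotheses. The point is still worth correcting, because even one discordant case would be conspicuous in a safety report.

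The conclusion assumes that INR results from liver follow-up reach the analysis data, as the flag in SAP 6.2.1 implies, and that the Output and Programming Specification does not already redefine the row.

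**What to change.** In SAP 4.5.3.1:

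1. Base the possible Hy's law row on the two criteria already flagged in 6.2.1: ALT ≥3×ULN with bilirubin ≥2×ULN and more than 35% direct; or ALT ≥3×ULN with INR >1.5, the latter not applied to participants on anticoagulants.
2. Keep the 28-day window for bilirubin and the allowance for missing direct bilirubin. Copying the protocol wording literally would lose both and could drop cases that are now counted. State how INR is paired in time with ALT, since neither document does.
3. Show the present rule (ALP <3×ULN or missing) as a separately labelled subset row. Use the same ALT and direct-bilirubin limits as the main row; otherwise a case at exactly 35% direct would fall in the subset but not in the row above it.

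The cost is one revised definition, one or two extra table rows and a check of anticoagulant use for any INR-route case. No new data collection is needed. The count may come out slightly higher than under the present rule.
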